### 5.2 Derived Efficacy Variables

In general, assessment total scores and subscores will be derived within the analysis datasets. In the event that total scores and/or subscores are also collected on the electronic case report from

(eCRF), the derived values will be used for all analyses. Both the raw and derived scores will be presented in listings.

### **5.2.1 Rett Syndrome Behaviour Questionnaire (RSBQ)**

The RSBQ is a 45-item caregiver-completed rating scale in which the caregiver rates items as “0” (Not True), “1” (somewhat or sometimes true) or “2” (very true). The RSBQ includes 8 subscales: 1) general mood, 2) breathing problems, 3) hand behavior, 4) face movements, 5) body rocking/expressionless face, 6) night-time behaviors, 7) fear/anxiety, and 8) walking/standing. The total score ranging from 0 to 90 will be calculated as the sum of the scores for all 45 items. Score for item 31 (Uses eye gaze to convey feelings, needs and wishes.) will be reversed (2-observed item score) in the calculation of total score and subscores. Higher total scores indicate greater frequency of symptoms. If there are 9 or less missing item scores, the total score will be calculated by the arithmetic mean of non-missing items multiplied by 45, rounded to the nearest integer. The RSBQ total score will be considered missing if there are missing scores for 10 or more items.

For the calculation of RSBQ subscores, the items under each RSBQ subscore will be summed. If an item is missing it will not be imputed and the subscore will be considered missing.

#### RSBQ Subscores

- 1) General mood consists of:
  - a. Abrupt changes in mood (Item 14)
  - b. Spells of screaming for no apparent reason during the day (Item 2)
  - c. There are times when she appears miserable for no apparent reason (Item 16)
  - d. Spells of inconsolable crying for no apparent reason during the day (Item 30)
  - e. There are times when she is irritable for no apparent reason (Item 29)
  - f. Screams hysterically for long periods of time and cannot be consoled (Item 22)
  - g. There are certain days/periods where she performs worse than usual (Item 15)
  - h. Vocalises for no apparent reason (Item 36)
- 2) Breathing problems consists of:
  - a. There are times when breath is held (Item 5)
  - b. Swallows air (Item 19)
  - c. Abdomen fills with air and sometimes feels hard (Item 25)
  - d. There are times when breathing is deep and fast (hyperventilation) (Item 1)
  - e. Air or saliva expelled from mouth with force (Item 6)
- 3) Hand behaviors consists of:
  - a. Does not use hands for purposeful grasping (Item 18)
  - b. Restricted repertoire of hand movement (Item 24)

- c. Hand movements uniform and monotonous (Item 20)
- d. The amount of time spent looking at an object is longer than time spent holding or manipulating them (Item 43)
- e. Has difficulty in breaking/stopping hand stereotypies (Item 35)
- f. Has frequent naps during the day (Item 21)

4) Repetitive face movements consists of:

- a. Makes mouth grimaces (Item 28)
- b. Makes repetitive tongue movements (Item 32)
- c. Makes grimacing expressions with face (Item 34)
- d. Makes repetitive movements involving fingers around tongue (Item 4)

5) Body rocking and expressionless face consists of:

- a. Rocks body repeatedly (Item 41)
- b. Expressionless face (Item 12)
- c. Rocks self when hands are prevented from moving (Item 33)
- d. Seems to look through people in to the distance (Item 17)
- e. Uses eye gaze to convey feelings, needs and wishes (reversed) (Item 31)
- f. Tendency to bring hands together in front of chin or chest (Item 40)

6) Night-time behaviours consists of:

- a. Spells of screaming for no apparent reason during the night (Item 13)
- b. Spells of inconsolable crying for no apparent reason during the night (Item 42)
- c. Spells of laughter for no apparent reason during the night (Item 37)

7) Fear/Anxiety consists of:

- a. Spells of apparent panic (Item 38)
- b. Spells of apparent anxiety/fear in unfamiliar situations (Item 7)
- c. Seems frightened when sudden changes in own body position (Item 9)
- d. There are times when parts of the body are held rigid (Item 10)

8) Walking/standing consists of:

- a. Walks with stiff legs (Item 39)
- b. Although can stand independently tends to lean on objects or people (Item 23)

Items not included in Subscores

- a. Makes repetitive hand movements with hands apart (Item 3)
- b. Grinds teeth (Item 8)
- c. Shifts gaze with a slow horizontal turn of head (Item 11)
- d. Spells of laughter for no apparent reason during the day (Item 26)
- e. Has wounds on hands as a result of repetitive hand movements (Item 27)
- f. Appears isolated (Item 44)
- g. Vacant ‘staring’ spells (Item 45)

### **5.2.2 Clinical Global Impression–Improvement (CGI-I)**

The CGI-I scale is used by the clinician to rate how much the subject's illness has improved or worsened relative to a baseline state. A 7-point scale is used from 1=very much improved, 2=much improved, 3=minimally improved, 4=no change, 5=minimally worse, 6=much worse, 7=very much worse.

Higher CGI-I scores denote more severe illness and less improvement in the illness respectively.

### **5.2.3 Communication and Symbolic Behavior Scales Developmental Profile™ Infant-Toddler Checklist – Social Composite Score (CSBS-DP-IT Social)**

The Checklist consists of 24 questions that range from 0 to 4 points within each of 7 Clusters. Credit of 0 points is given for items checked “Not Yet”, 1 point for items checked “Sometimes”, or 2 points for items checked “Often”. For items that describe a series of numbers or ranges, credit of 0 points is given for items checked “None” and 1 to 4 points for items containing numbered choices.

Three composite scores assessing 7 skill areas can be calculated. The Social Composite score is comprised of 13 items in the skill areas “Emotion and Eye Gaze” (items 1 to 4), “Communication” (items 5 to 8), and “Gestures” (items 9 to 13). The Speech Composite score, including the skill areas “Sounds” and “Words” is based on items 14 to 18. The Symbolic Composite score, including the skill areas “Understanding” and “Object Use”, is based on items 19 to 14.

The Social Composite raw score (comprised of items 1 to 13) ranging from 0 to 26 will be calculated as the sum of the scores for all 13 items. Higher Social Composite raw scores indicate better social communication development. If there are 2 or less missing item scores, the Social Composite raw score will be calculated by the arithmetic mean of the non-missing item scores multiplied by 13, rounded to the nearest integer. The Social Composite raw score will be considered as missing if there are missing scores for 3 or more items.

### **5.2.4 Overall Quality of Life Rating of the Impact of Childhood Neurologic Disability (ICND) Scale**

The numeric scale of the child's overall quality of life ranges from 1 (“Poor”) to 6 (“Excellent”); lower overall quality of life scores indicate lower quality of life. Only the quality of life assessment will be collected.

### **5.2.5 Rett Syndrome Clinician Rating of Hand Function (RTT-HF)**

The RTT-HF is a clinician completed clinical assessment of the subject's ability to use her hands for functional purposes. The assessment is made on an 8-point Likert scale (0-7) with 0 denoting normal functioning and 7 the most severe impairment.

### **5.2.6 Rett Syndrome Clinician Rating of Ambulation and Gross Motor Skills (RTT-AMB)**

The RTT-AMB is a clinician completed clinical assessment of the subject's ability to sit, stand, and ambulate. The assessment is made on an 8-point Likert scale (0-7) with 0 denoting normal functioning and 7 the most severe impairment.

### **5.2.7 Rett Syndrome Clinician Rating of Ability to Communicate Choices (RTT-COMC)**

The RTT-COMC is a clinician completed clinical assessment of the subject's ability to communicate her choices or preferences, which can include the use of nonverbal means such as eye contact or gestures. The assessment is made on an 8-point Likert scale (0-7) with 0 denoting normal functioning and 7 the most severe impairment.

### **5.2.8 Rett Syndrome Clinician Rating of Verbal Communication (RTT-VCOM)**

The RTT-VCOM is a clinician completed clinical assessment of the subject's ability to communicate verbally. The assessment is made on an 8-point Likert scale (0-7) with 0 denoting normal functioning and 7 the most severe impairment.

### **5.2.9 Clinical Global Impression–Severity (CGI-S)**

The CGI-S is a 7-point scale that requires the clinician to rate the severity of the subject's illness at the time of assessment, relative to the clinician's experience with subjects who have the same diagnosis. Considering total clinical experience, a subject is assessed on severity of illness at the time of rating: 1=normal, not at all ill; 2=borderline ill; 3=mildly ill; 4= moderately ill; 5=markedly ill; 6=severely ill; or 7=extremely ill.

Higher CGI-S scores denote more severe illness and less improvement in the illness respectively.

### **5.2.10 Rett Syndrome Caregiver Burden Inventory (RTT-CBI)**

The RTT-CBI consists of 24 negatively worded items (Items 1 through 24). Frequency ratings are on a 5-point Likert scale including: 0=never; 1=rarely; 2=sometimes; 3=frequently and 4=nearly always. The RTT-CBI also includes 2 positively worded items (items 25 and 26) that comprise the Optimism Index; this index will not be used for analysis. The total score ranging from 0 to

96 will be calculated as the sum of the scores for Items 1-24. If there are 4 or fewer missing item scores, the RTT-CBI total score will be calculated by the arithmetic mean of the non-missing item scores multiplied by 24, rounded to the nearest integer. The RTT-CBI total score will be considered as missing if there are missing scores for 5 or more items.

### **5.3 Study Day**

If the date of assessment occurs on or after the first dose date, then study day will be calculated as (date of assessment – date of first dose) + 1. If the date of assessment occurs prior to the first dose date, then study day will be calculated as (date of assessment – date of first dose). There is no study day 0.

### **5.4 Baseline Definition**

Data from the latest predose value of (Study ACP-2566-004 Week 40/EOT visit, unscheduled visit within Week 40 window, or Study ACP2566-005 Baseline Visit) will be carried over as Baseline information in the present study, as applicable (e.g., not for the CGI-I for which this is not applicable).

### **5.5 Analysis Visit Windows**

Efficacy and safety will be summarized by analysis visit as presented in Table 2 below.

**Table 2 Analysis Visit Windows**

Analysis Visit	Target Study Day	Study Day Interval
Baseline (Day 1)	1	$\leq 1$
Day 1 Post First Dose*	1	1
Week 12	85	2 – 224
Week 52	365	225 – 546
Week 104	729	547 – 819
Week 130	911	820 – 940

\*For ECG assessments only; other assessments post-first dose on Day 1 will go to the Week 12 analysis visit window.

#### **5.5.1 Unscheduled Assessments**

Both Scheduled and Unscheduled assessments, including the assessments at early termination visits, will be included for planned timepoint analyses based on the above analysis visit windowing rules. All assessments will be presented in data listings.

### **5.5.2     Multiple Measurements within Visit Windows**

In the event that more than one assessment falls within a given window, the assessment closest to the target study day will be selected for the by-visit analysis. If two assessments are equidistant from the target study day, then the chronologically last assessment will be used.

For safety analyses where the extreme values should be selected (e.g., overall post-Baseline minimum, overall post-Baseline maximum, and potentially clinically important values), all non-missing post-Baseline values should be considered, regardless of whether the value is selected for the by-visit summaries. All assessments will be presented in data listings.

### **5.6       Missing or Incomplete Date for Last Dose of Study Drug**

For subjects with completely missing last dose date, the last dose date will be imputed by the last expected dosing date, defined as the earliest of the following dates: last drug kit dispense date + scheduled dosing interval per protocol, EOT/ET date and the return date of the last dispensed drug kit.

For subjects with partial missing last dose date, the imputation will be compared against the last expected dosing date as defined above. Detailed algorithms will be documented in a separate programming specifications document. The missing or incomplete dates will be displayed in the data listings as reported on the eCRF rather than the imputed dates.

### **5.7       Missing or Incomplete Dates for Prior or Concomitant Medications**

Missing or incomplete medication start or stop dates will be imputed for the purpose of determining whether the medication is taken concomitantly or not (see [Section 11](#) for definition). When the chronological order of medication use relative to the study drug treatment period is unclear due to missing or incomplete date(s), the medication will be considered as concomitant. The imputation algorithms will be detailed in the analysis dataset specification document. The missing or incomplete dates as captured on the eCRF will be displayed in the data listings.

### **5.8       Missing or incomplete Date for Adverse Events**

Missing or incomplete adverse event (AE) start dates will be imputed for the purpose of determining whether the AEs are treatment-emergent or not (see [Section 14.2](#) for definition). When the chronological order of an AE onset relative to the study drug treatment period is unclear due to missing or incomplete date(s), the AE will be considered as treatment-emergent. The imputation algorithms will be detailed in the analysis dataset specification document. The missing or incomplete dates captured on the eCRF will be displayed in the data listings.

### **5.9 Missing Severity Assessment for Adverse Events**

If the severity is missing for an AE starting on or after the date of the first dose of study drug, then a severity of “Severe” will be assigned. The imputed values for severity assessment will be used for incidence summaries, while the actual values will be used in data listings.

### **5.10 Missing Relationship to Study Drug for Adverse Events**

If the relationship to study drug is missing for an AE starting on or after the date of the first dose of study drug, a causality of “Related” will be assigned. The imputed values for relationship to study drug will be used for incidence summaries, while the actual values will be presented in data listings.

### **5.11 Character Values of Clinical Laboratory Variables**

If the reported value of a clinical laboratory variable cannot be used in a statistical analysis due to, for example, a character string reported for a numeric variable, an appropriately determined coded value may be used in the statistical analysis. The coding algorithms will be detailed in the analysis dataset specification document. The actual values as reported in the database will be presented in data listings.

## **6. SUBJECT DISPOSITION**

The number of sites that enrolled at least 1 subject and the number of subjects screened will be tabulated. In addition, the number of subjects enrolled at each site will also be tabulated by Safety Analysis Set.

The number and percentage of subjects who completed the study, discontinued early (all discontinued and by discontinuation reasons including reason due to the COVID-19 public health emergency (PHE), and the reason for discontinuation will be summarized using the Safety Analysis Set.

The number of caregivers who consented and participated in the optional exit interview, and the number of subjects who took commercially marketed trofinetide within 30 days after study completion will also be summarized using the Safety Analysis Set.

## **7. PROTOCOL DEVIATIONS**

Protocol deviations will be reviewed periodically over the course of the study. The review process, definition of the deviation categories, and the classification of a deviation as major or minor are detailed in the Protocol Deviation Management Plan. Protocol deviations will also be assessed with respect to relationship to the COVID-19 PHE. A summary of the number and percentage of subjects with major protocol deviations for each deviation category will be presented for the Safety Analysis Set in three ways: all protocol deviations, COVID-19-PHE related protocol deviations, and non-COVID-19-PHE related protocol deviations. Three data listings of all protocol deviations, COVID-19-PHE related protocol deviations, and non-COVID-19-PHE related protocol deviations will be provided.

## **8. DEMOGRAPHICS AND BASELINE CHARACTERISTICS**

Demographics and baseline characteristics will be summarized for the Safety Analysis Set using descriptive statistics, using the baseline for this study. Variables include, but are not limited to, age, age group (5-10 years old, 11-15 years old, and  $\geq$  16 years old), race, ethnicity, height, weight, BMI, Baseline RSBQ total score, Baseline RSBQ severity (< 35 total score and  $\geq$  35 total score), and Baseline CGI-S score.

Race will also be categorized by White vs. Non-White. The reported age reflects a subject's age at the informed consent date of this study. Baseline characteristics for subjects in ACP-2566-005 will also be summarized using the baseline of the antecedent DB study ACP-2566-003 separately.

## **9. MEDICAL HISTORY**

Medical history reported terms will be coded with Medical Dictionary for Regulatory Activities (MedDRA), version 23.0 or newer. The subject incidence will be summarized for each system organ class (SOC) and preferred term for the Safety Analysis Set. A subject will be counted only once per SOC or per preferred term for the summary. A listing of the SOC, preferred term, body system, verbatim for the medical history condition/event, start and stop dates (when available), and an indicator for whether or not the condition is ongoing will be provided.

## **10. EXTENT OF EXPOSURE AND TREATMENT COMPLIANCE**

Extent of exposure and treatment compliance will be summarized as both continuous variables and categorical variables for Safety Analysis set.

### **10.1 Exposure to Study drug**

Duration of exposure to study drug will be calculated for each subject as (last dose date – first dose date + 1). The number and percentage of subjects within each of the following exposure levels in terms of duration of exposure will also be tabulated: <12 weeks (1 to 83 days), 12 to <52 weeks (84 to 363 days), 52 to <104 weeks (364 to 727 days), 104 to <130 weeks (728 to 909 days), and >=130 weeks (910 days or longer).

### **10.2 Measurement of Treatment Compliance**

The study drug is provided in liquid form supplied in a 500 mL bottle. Study drug compliance will be calculated based on the drug accountability and dose modification data as collected on the eCRF. The study drug compliance will be calculated as (the total volume of drug actually taken (in mL) divided by the total volume of drug expected to be taken)\*100.

The total volume of drug expected to be taken will be based on the duration of exposure and dosing schedule as in [Table 3](#). However, if there is any dose modification prescribed by the investigator due to intolerance, the total drug expected to be taken will be adjusted accordingly to account for the modified prescribed dose schedule as recorded in the EDC.

The total volume of drug actually taken will be calculated as (total drug dispensed – total drug returned (height in cm of drug remaining converted into volume in mL based on the following conversion [Table 4](#)).

Treatment compliance will be summarized as a categorical variable. The number and percentage of subjects within each of the following compliance levels will be tabulated: <80%, 80 to 120% and >120%.

Details of treatment compliance calculation are provided in a separate programming specifications document.

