5.1.3 Dosing and Administration

5.1.3.1 Dosing

The subject's assigned dose for this study will be the final dose from the antecedent study. If the subject's weight at the Baseline visit of the present study puts them in a new weight category (see Table 5–1), the Investigator may decide to increase the dose to the dose associated with the new weight category. Similarly, if the subject's weight after 52 weeks in the present study, or thereafter puts them in a new weight category, the Investigator may decide to increase the dose to the dose associated with the new weight category.

The dose may be decreased during the study for poor tolerability as discussed in [Section 5.1.3.2](#). Study drug is administered twice a day, once in the morning and once in the afternoon or evening. There should be at least 8 hours between doses. The study drug may be given with or without food.

Table 5–1 Weight-Dosing Categories

Weight	Dose	Total Daily Dose
12-20 kg	30 mL (6 g) BID	60 mL (12 g)
>20-35 kg	40 mL (8 g) BID	80 mL (16 g)
>35-50 kg	50 mL (10 g) BID	100 mL (20 g)
>50 kg	60 mL (12 g) BID	120 mL (24 g)

Abbreviation: BID=twice daily

Since all subjects in this study are known to have taken trofinetide without developing an unacceptable prolongation of the QT interval, there is no requirement to perform an ECG 2-3 hours after the first dose.

The day the first dose is taken will be considered Day 1 of dosing.

Investigational product will be shipped directly to the subject. Confirmation of any delivery to the subject will be made by a visiting nurse. Study drug shipment, return, and accountability will be performed in accordance with the drug distribution plan. In addition,

study drug will be dispensed at the site during the Baseline visit when the visit is conducted in the clinic.

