6.3 Caregiver Diary

A semi-structured caregiver diary will be completed during treatment in which caregivers will record seizures and seizure-like spells if they are present.

At the Baseline visit, the clinician will review subject's seizure profile (if applicable) and will, if necessary, update the characterization of the subject's typical seizure types. These are recorded in the caregiver diary. Dose modifications and missed or partial doses will be recorded in the caregiver diary.

The caregiver diary will be completed and collected on an ongoing basis throughout the study from Baseline to EOT/ET. The clinician will verbally ask about AEs (see [Section 7.4.1](#)), review the events recorded in the diary with the caregiver and will make a clinical evaluation, including an evaluation of whether an AE will be reported.

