### **Open-label Treatment Period**

The EOT visit of the antecedent trofinetide study (e.g., ACP-2566-004) serves as the Baseline visit (Visit 1) of the present study. The day the first dose is taken will be considered Day 1 of dosing. Dosing is twice a day, once in the morning and once in the evening.

The subject’s assigned dose for this study will be the final dose from the antecedent study. If the subject’s weight at the Baseline visit of the present study puts them in a new weight category ([Table 1](#)), the Investigator may decide to increase the dose to the dose associated with the new weight category. Similarly, if the subject’s weight after 52 weeks in the present study, or thereafter puts them in a new weight category, the Investigator may decide to increase the dose to the dose associated with the new weight category.

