**Table 3 Dosing Schedule and Total Expected Volume Based on Weight at Baseline of the Present Study**

Weight	Dose	Total Daily Dose	Total Expected Volume
12-20 kg	30 mL (6 g) BID	60 mL (12 g)	60 mL x Number of Days Expected to be Dosed
>20-35 kg	40 mL (8 g) BID	80 mL (16 g)	80 mL x Number of Days Expected to be Dosed
>35-50 kg	50 mL (10 g) BID	100 mL (20 g)	100 mL x Number of Days Expected to be Dosed
>50 kg	60 mL (12 g) BID	120 mL (24 g)	120 mL x Number of Days Expected to be Dosed

BID = twice daily

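### The compliance denominator follows the Baseline-weight dose and is corrected only for intolerance, so fully adherent subjects on another prescribed dose get a biased and sometimes misclassified result

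*SAP*

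**What the plan says.** SAP 10.2 defines compliance as 100 times volume taken divided by volume expected. Expected volume is built from duration of exposure and the Table 3 schedule, and Table 3 is titled "Dosing Schedule and Total Expected Volume Based on Weight at Baseline of the Present Study". One correction is described: "if there is any dose modification prescribed by the investigator due to intolerance, the total drug expected to be taken will be adjusted accordingly". The result is tabulated as <80%, 80 to 120% and >120%. The introduction to SAP 10 asks for more: "Extent of exposure and treatment compliance will be summarized as both continuous variables and categorical variables for Safety Analysis set". SAP 10.2 closes with "Details of treatment compliance calculation are provided in a separate programming specifications document", a document that is not available here.

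The prescribed dose follows a different rule. Under Protocol 5.1.3.1 the subject's "assigned dose for this study will be the final dose from the antecedent study". If weight at Baseline falls in a new category, the investigator may raise the dose but need not. SAP 3.1 repeats this and allows the same choice when the subject's "weight after 52 weeks in the present study, or thereafter puts them in a new weight category". No weight-based decrease is described.

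**The concern.** A compliance ratio should compare what was taken with what was prescribed. As written, the denominator departs from the prescription in two situations that the protocol permits:

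1. The carried-over dose is not the Table 3 dose for the subject's Baseline weight.
2. The dose is raised for weight after Week 52.

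Neither is a modification for intolerance. In both, an investigator's dosing decision would be reported as under-use or over-use by the family, and real under-use could pass as adequate. The second situation is foreseeable: the age groups in SAP 8 start at 5 to 10 years, and treatment lasts up to about 32 months.

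Some cases are not affected. A carried-over dose that already matches Table 3 gives no error, nor does an increase at Baseline to the Table 3 dose. A carried-over reduced dose is affected only if the earlier reduction is not recorded as a modification in this study.

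**Working it through.** **Inputs.** Daily volumes from SAP Table 3; compliance bands from SAP 10.2; Week 52 = 364 days, Week 104 = 728 days and Week 130 = 910 days from the exposure bands in SAP 10.1. Months are converted at 365.25/12 days (SAP 5.1): 23 months = 700 days, 29 months = 883, 32 months = 974. Day 917 is Week 130 plus its 7-day visit window. Every case except the masking cases assumes that the subject takes exactly the prescribed volume.

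**Table 3 reproduces.** Twice the BID volume is 2 × 30, 40, 50, 60 = 60, 80, 100, 120 mL/day. At 1 g per 5 mL this is 12, 16, 20, 24 g, as printed.

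**Carried-over dose differs from Table 3 for the whole study.** Compliance = prescribed / Table 3.

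| Prescribed (mL/day) | Table 3 (mL/day) | Compliance | Band |
|---|---|---|---|
| 60 | 80 | 75.0% | <80% |
| 80 | 100 | 80.0% | 80 to 120% |
| 100 | 120 | 83.3% | 80 to 120% |
| 80 | 60 | 133.3% | >120% |
| 100 | 80 | 125.0% | >120% |
| 120 | 100 | 120.0% | 80 to 120% |

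**Increase from a to b mL/day after day 364, with D days of dosing.** Compliance = (364a + (D − 364)b) / (D × a). For 60 to 80 at D = 910: (364 × 60 + 546 × 80) / (910 × 60) = 65,520 / 54,600 = 120.0%.

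| Change | D = 700 | D = 910 | D = 974 |
|---|---|---|---|
| 60 to 80 | 116.0% | 120.0% | 120.9% |
| 80 to 100 | – | 115.0% | 115.7% |
| 100 to 120 | – | 112.0% | 112.5% |
| 60 to 100 | 132.0% | 140.0% | – |
| 80 to 120 | 124.0% | 130.0% | – |

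(– = not calculated.)

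- Among one-category increases only 60 to 80 leaves the band, and only beyond D = 364 × 20/8 = 910 days. It gives 119.6% at 883 days and 120.1% at 917.
- Every two-category value shown is >120%.

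**Increase after day 728.** Same formula with 728 in place of 364, D = 910: 106.7%, 105.0%, 104.0%, 113.3% and 110.0%, in the row order above. All are in band.

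**Masking.** The true adherence that reads as 80% is 80% divided by the inflation factor.

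- Carry-over, 80 against Table 3 60: 80/1.333 = 60.0%.
- Carry-over, 100 against 80: 80/1.25 = 64.0%.
- One-category increase after day 364, D = 910, with under-use uniform over time: 80/1.20 = 66.7%, 80/1.15 = 69.6%, 80/1.12 = 71.4%.

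**With expected volume set to the prescribed volume,** a fully adherent subject reads 100% in every case above.

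**The case against.** The case on the other side has five parts.

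- **Data source.** SAP 10.2 opens by saying that compliance uses drug accountability and eCRF dose modification data, with no restriction on reason. That suggests that weight-based changes are recorded, so the data may well exist. It does not state when the denominator changes; the sentence that does names only intolerance.
- **Table title.** SAP Table 1 carries the same Baseline-weight label, yet SAP 3.1 uses its categories for later weights too. The title alone is therefore weak evidence of a frozen denominator. The intolerance-only clause remains.
- **Programming specification.** It may already use the prescribed dose. If so, it departs from the SAP; if it follows the SAP, it produces the error. The wording needs correcting either way.
- **Rarity of the large errors.** This stands in part. The 125.0% and 133.3% figures need a carried-over dose above the row for Baseline weight. The 75.0% figure needs the optional increase to be declined throughout. A two-category increase needs a move from at most 20 kg to above 35 kg, or from at most 35 kg to above 50 kg, a gain of more than 15 kg. The ordinary one-category increase stays in band at 910 days, and at the 29 months anticipated for the first entrant 60 to 80 gives 119.6%.
- **Reporting and weight.** SAP 10.2 itself mentions only a categorical summary, so in-band shifts might seem invisible. The introduction to SAP 10 requires a continuous summary as well, and there they would appear. Compliance is indeed only descriptive: it defines no analysis set and feeds no endpoint.

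**Conclusion.** The rule as written gives the wrong denominator for dosing that the protocol allows. With full adherence, a carried-over dose one category away from Table 3 reads 75.0 to 83.3% when it is lower and 120.0 to 133.3% when it is higher; three of the six combinations fall outside the band. A one-category increase after Week 52 inflates compliance by 12 to 20 percentage points at 910 days without leaving the band. Two-category increases at that time leave it.

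These figures assume that the SAP text is applied literally and that increases take effect right after day 364 or day 728. The number of affected subjects cannot be derived from the documents. The consequence is confined to the compliance summaries: exposure duration in SAP 10.1 depends only on first and last dose dates, and the primary safety endpoints do not use compliance. It should be corrected, but it does not threaten the study's main conclusions. Confidence is medium, because the programming specification could not be seen.

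**What to change.** In SAP 10.2, define expected volume as the sum over treated days of the daily volume prescribed and recorded in the EDC. It should start from the assigned starting dose and follow every investigator-authorised change, whatever the reason. Keep Table 3 as a reference only, and bring the programming specification into line. This changes the analysis denominator and no dosing rule.

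The cost is wording, programming and one check of data capture. Protocol 6.3 states "Dose modifications and missed or partial doses will be recorded in the caregiver diary", and SAP 10.2 refers to eCRF dose modification data, so weight-based increases are probably available. No passage confirms this explicitly, or that the carried-over starting dose is recorded. The action-taken list in Protocol 7.2.5 has no entry for an increase, but it concerns adverse events and settles little. Confirm both items before the programming is finalised.
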